1.3 Schedule of activities

The SoAs provide an overview of the protocol visits and procedures. The investigator may schedule visits (unplanned visits) in addition to those listed in the SoAs, in order to conduct evaluations or assessments required to protect the wellbeing of the trial subjects.

Activity		Visit 0	Visit 1	Visit 2	Visit 4	Visit 5	Visit 6 ^k	Visit 7 ^k	Early termination
W	eek(s)			1	4	7	12	26	
	Day	-30 to -1	1	8+2	29±7	50±7	85±10	182±20	
		(Screening)	(Day of inj. 1; pre-dose except IMP injection)	(~7 d post inj.)	(~28 d post inj.)	(~49 d post inj.)	(~84 d post inj.)	(~181 d post inj. EOT Visit)	
Collect informed consent		Х							
Assess inclusion/exclusion criteria compliance		Х	X (review)						
Collect demographic and medical history		Х	X (update)						
Physical examination		Х	X a	X a	X a			X a	X a
Vital signs, body weight ^b		Х	Хc	Х	Х			х	Х
Urine pregnancy test for WOCBP		Х	х					х	х
Urine for clinical laboratory ^d		Х	х		Х			х	х
Blood draws for clinical laboratory (15 mL) ^e		Х	х		Х			х	Х
Allocation and randomization to IMP			х						
IMP injection, then observe subjects for ~1 h			х						
Subject hotline availability		Start	=>	=>	=>	=>	=>	End	(End)
Oral swabs for NAAT-based SARS-CoV-2 for screen	ing ^f	Xg	X a						
Oral swabs for NAAT-based SARS-CoV-2 for surveill	ance			Х	Х	Х	Х	х	х
Oral swabs for SARS-CoV-2 sequencing ^h		Xg	Хa	Х	Х	Х	Х	х	х

Table 1: Schedule of events for Group A (with one injection of either Comirnaty or BNT162b2s01)

Activity	Visit 0	Visit 1	Visit 2	Visit 4	Visit 5	Visit 6 ^k	Visit 7 ^k	Early termination
Week(s)			1	4	7	12	26	
Day	-30 to -1	1	8+2	29±7	50±7	85±10	182±20	
	(Screening)	(Day of inj. 1; pre-dose except IMP injection)	(~7 d post inj.)	(~28 d post inj.)	(~49 d post inj.)	(~84 d post inj.)	(~181 d post inj. EOT Visit)	
Blood draws for NATAB and nucleocapsid protein testing (15 mL)		х	х	Х		Х	х	х
Blood draws for CMI (120 mL each)		Х	Х			Х	х	Х
Issue/collect subject diaries		X (issue)	X (collect)					
Subjects report daily reactogenicity (incl. body temperature) in their diary on Day 1 and for 7 d post each vaccination		X (post- dose) ^j	х					
Record AEs since last visit		х	Х	Х	Xi	Xi	Xi	X ⁱ
Record pregnancies		Start	=>	=>	=>	=>	End	(End)
Record concomitant medication		Х	Х	Х	XI	XI	XI	XI

Note: The SoA allows for ad hoc SARS-CoV-2 testing for symptomatic or asymptomatic subjects.

a Brief (symptom-directed) physical examination; no height measurement.

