- m If applicable, Visit 7 or Visit 6 should be used to inform Group B transplant subjects (Cohort 13 of the BNT162-01 trial) on Dose 2 and informed consent must be collected. If Visit 6 is applicable, then Visit 7 must be skipped. Thereafter the SoA in Table 2a is applicable.
- n Record any non-trial SARS-CoV-2 vaccinations that trial subjects receive during the trial in the CRF until the last trial visit.
- o If a transplant subject consents to receive a second vaccination (i.e., 4th dose since the parent trial), the SoA in Table 2a is then applicable, there will be no blood sampling for CMI testing at the visit of consent (Visit 6 or Visit 7).
- p Only for Group B transplant subjects: record any non-trial SARS-CoV-2 vaccinations that trial subjects receive in the CRF.

Abbreviations: AE = adverse event; AESI = adverse event of special interest; CMI = cell mediated immunity; CRF = case report form; d = day; ELISA = enzyme-linked immunosorbent assay; EOT = end of trial; h = hour(s); IMP = investigational medicinal product; inj. = (IMP) injection; NAAT = nucleic acid amplification-based test; NATAB = neutralizing antibody titers and antibody binding; SAE = serious adverse event; SRC = safety review committee; SARS-CoV-2 = the virus leading to COVID-19; SoA = schedule of activities; WOCBP = women of childbearing potential.

BioNTech SE	Clinical Trial Protocol	Page 15 of 91 Version: 4.0
Confidential	BN1162-14	Date: 20 JAN 2022

Table 2a: Schedule of events for Immunology Subgroup of Group B transplant subjects (injection 2)

Activity	Visit 8	Visit 9	Visit 10	Visit 11 ^g	Visit 12 ^g	Early termination
Week(s) (post-Dose 2)		1	4	12	26	
Day (post-Dose 2)	1	8+2	29±7	85±10	182±20	
	(3 to 7 months post inj. 1; pre-dose except inj. 2)	(~7 d post inj. 2)	(~28 d post inj. 2)	(~3 months post inj. 2)	(~6 months post inj. 2 EOT Visit)	
Collect informed consent						
Assess inclusion/exclusion criteria compliance						
Collect demographic and medical history						
Physical examination	X ^a	X ^a			X a	X a
Vital signs, body weight ^b	X c					
Urine pregnancy test for WOCBP	Х					Х
Blood draw for hematology testing (up to 3 mL) $^{\rm d}$	Х	Х	Х			
Allocation to IMP						
IMP injection, then observe subjects for ~1 h	Х					
Subject hotline availability	=>	=>	=>	=>	End	(End)
Oral swab for NAAT-based SARS-CoV-2 testing for surveillance	×	х	х	х	Х	×
Oral swab for SARS-CoV-2 sequencing ^e	Х	Х	х	Х	Х	Х
Blood draws for NATAB and nucleocapsid protein testing (15 mL)	×	х	х	х	х	x

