7 DISCONTINUATION OF TRIAL TREATMENT AND TRIAL SUBJECT DISCONTINUATION/WITHDRAWAL

7.1 Discontinuation of trial treatment

7.1.1 Criteria to permanently discontinue IMP administration for Group B

Note that discontinuation from IMP does not represent withdrawal/discontinuation from the trial. Trial subjects permanently discontinued from IMP administration should still complete all assessments planned in the SoA (Section 1.3).

Reasons for definitive discontinuation from IMP include the following:

- SAEs warranting discontinuation;
- other trial-related safety concerns;
- subject or investigator request;
- pregnancy;
- deterioration in trial subject health at the time of IMP injection (at the discretion of the investigator).

In the event of trial subject permanent discontinuation from IMP, it must be documented on the appropriate CRF/in the medical records if the trial subject is discontinuing further receipt of trial treatment, or also from trial procedures, post-treatment follow-up, future collection of additional information and/or consent.

7.1.2 Criteria for temporarily delaying enrollment, randomization for Group A, or administration of IMP

The are no criteria defined which trigger temporarily delaying trial subject enrollment or randomization.

There are medical conditions or situations which may delay administration of IMP as follows:

- Current febrile illness (body temperature ≥38.0°C) or other acute illness within 48 h before IMP administration.
- Confirmed SARS-CoV-2 infection; vaccination should still proceed as soon as medically indicated but ideally no later than 12 weeks after resolution of any serious COVID-19 symptoms at the discretion of the investigator.
- The second Comirnaty injection (injection 2) may also be delayed for medical reasons (e.g., influenza vaccination) and such delays should be as short as possible, e.g., ≤3 weeks for non-live or attenuated vaccines, ≤5 weeks for live attenuated vaccines, ≤12 weeks if SARS-CoV-2 infection is confirmed, etc., with the exception of Group B transplant subjects who will receive their injection 2 based on SRC recommendation.

BioNTech SE
Confidential

• The circumstances leading to the delay and the resulting delay should be discussed with the sponsor's Medical Monitor.

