1.1. Objectives and endpoints

Table 2: Objectives and endpoints

Objectives	Endpoints
Primary	
To determine the safety and tolerability of one or two boosting doses of Comirnaty or one dose of BNT162b2s01 in BNT162- 01 trial subjects, or two boosting doses of Comirnaty in BNT162-04 trial subjects.	 For all Group A and Group B subjects: The proportion of subjects in each treatment group with at least one SAE or the proportion of AESIs occurring up to 26 weeks after the first IMP injection. For Group A and a selected subset of Group B subjects: The frequency of solicited local reactions (pain, tenderness, erythema/redness, induration/swelling) at the injection site recorded up to 7 days after each IMP injection. The frequency of solicited systemic reactions (vomiting, diarrhea, headache, fatigue/tiredness, fever, chills, nausea, new or worsened muscle pain, new or worsening joint pain) recorded up to 7 days after each IMP injection. The proportion of subjects with at least one unsolicited TEAE occurring up to 28 days after IMP injection in each treatment group.

Objectives	Endpoints
Secondary	
To describe changes in SARS-CoV-2 neutralizing antibody titers from baseline to reference and SARS-CoV-2 variant B.1.351.	 For Group A and Group B subjects (except transplant subjects): Antibody titers to recombinant S1 and RBD protein derived from reference and SARS-CoV-2 variant B.1.351** will be assessed at baseline (Day 1) and then Day 8, Weeks 3*, 4, 7*, 12, and 26: Neutralizing antibody titers. Antibody titers (ELISA). SARS-CoV-2 functional cross-neutralization of variant B.1.351** to reference strain.
	 * Group B only ** Group A only For Group B transplant subjects only: Antibody titers to recombinant S1 and RBD protein derived from SARS-CoV-2 will be assessed at baseline (Day 1) and then Day 8, Weeks 4, 12, and 26 post Dose 1, and at Dose 2 (Day 1) and then Day 8, Weeks 4, 12 and, 26 post Dose 2: Neutralizing antibody titers Antibody titers (ELISA)
Exploratory	

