	Group B immunology subset and will receive one injection of Comirnaty [®] which could be potentially followed 3 to 7 months afterwards by a second injection of Comirnaty [®] . This group will be referred to as Group B transplants. Subjects not eligible during this period due to any medical reason (e.g., breakthrough infection causing investigational medicinal product delay decision from the investigator) will not receive the 4 th dose in this trial. Dose : 30 µg of Comirnaty [®] or BNT162b2s01 Dosing regimen: Group A: One (at Day 1) intramuscular injection with 30 µg of either Comirnaty or BNT162b2s01. Group B: Two (at Day 1 and Day 21) intramuscular injections with 30 µg of Comirnaty, except Group B transplant subjects. Group B transplant subjects: Two intramuscular injections of 30 µg of Comirnaty, with injection 2 administered 3 to 7 months after injection 1 (Day 1). The planned time points for injection of the investigational medicinal product for Groups A and B are provided in the Schedule of Activities in the protocol (Section 1.3)
	Administration route: Intramuscular
Treatment and study duration	In total, the planned trial duration for a subject in this trial is approximately 30 weeks (≤4 weeks of screening and ~26 weeks follow-up).
Planned number of subjects	The maximum number of subjects in Group A will be 90 (including up to 15 HIV-positive subjects) and in Group B will be 459 (including up to15 transplant subjects). A subset of Group B (n=129) will be asked to participate in an immunology subset evaluation.
Randomization and blinding	Subjects in Group A will be randomized in a 2:1 ratio to either BNT162b2s01 or Comirnaty [®] . All subjects in Group B will receive at least one injection of Comirnaty [®] . They will not be randomized. The study is open-label.

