6.1.2. Definitions and derivations

Unscheduled visits

Unscheduled visits will not be included in the summary tables but will be included in the listings.

Variables

Unless otherwise specified, **baseline** is defined as last value prior to first injection of IMP (Dose 1) given in this BNT162-14 trial on Day 1, including unscheduled visits.

Change from baseline will be calculated as follows:

• Change from baseline = post-baseline assessment value – baseline assessment value.

Duration [days] will be calculated as follows:

• Duration [days] = last observation date – first observation date + 1

Time from first injection (Dose 1) to first reaction will be calculated as follows: Time from first injection to first reaction [days] = first reaction date – date of first injection (Dose 1) + 1

Time from first reaction to last reaction will be calculated as follows:

Time from first to last reaction [days] = last reaction date – first reaction date + 1

Days since last injection will be calculated as follows:

Days since last injection = onset date of AE – date of last injection +1

For conversion of days to months or years the following rules will be applied:

- 1 month = 30.25 days
- 1 year = 365.25 days

Study Day and are defined as follows:

- Study day:
 - If study date < date of first injection (Dose 1), then study day = study date date of first injection
 - If study date >= date of first injection (Dose 1), then study day = study date date of first injection + 1

Fold rise will be calculated as follows:

• Fold rise = post-dose value / baseline value

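### Table 2 footnote m drops Visit 7 at consent rather than at dosing, so a transplant subject who consents at Visit 6 and is then not dosed has no assured Week 26 visit

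*Protocol*

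**What the plan says.** Three footnotes to Table 2 (Protocol 1.3) govern the hand-over of transplant subjects from Table 2 to Table 2a.

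- **Footnote h** keeps them on Table 2, leaves the timing of the second vaccination to the SRC, and then sends them to Table 2a. Read in order, the change of schedule follows the vaccination.
- **Footnote m** makes Visit 6 or Visit 7 the consent visit for Dose 2. It adds "If Visit 6 is applicable, then Visit 7 must be skipped", and ends by making Table 2a the schedule from then on.
- **Footnote o** says that if a transplant subject "consents to receive a second vaccination (i.e., 4th dose since the parent trial), the SoA in Table 2a is then applicable".

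Table 2a opens with Visit 8, described as "3 to 7 months post inj. 1; pre-dose except inj. 2". Visits 9 to 12 are all counted in days after Dose 2.

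The case of no second dose is foreseen. SAP 1.2 refers to "Subjects not eligible during this period due to any medical reason (e.g., breakthrough infection causing investigational medicinal product delay decision from the investigator" and says that they do not receive the fourth dose in this trial. Protocol 7.1.1 says that subjects taken off IMP "should still complete all assessments planned in the SoA".

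Two endpoints reach Week 26 after Dose 1 for these subjects: the primary SAE/AESI endpoint, and the secondary neutralizing and ELISA titers (Protocol 3, SAP 1.1).

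**The concern.** The skip makes sense for a subject who goes on to receive injection 2, because Table 2a then supplies a full new set of dated visits. But the rule is triggered by consent, and consent at about Day 85 can precede the dose by months. A subject who consents and then becomes ineligible has given up Visit 7 and has no Dose 2 date from which Visits 9 to 12 can be counted.

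At stake are the scheduled adverse event inquiry at the end of the 26-week primary period and the Week 26 post-Dose-1 titer. Only subjects not yet given injection 2 can supply a Week 26 titer unaffected by it, and the rule removes the visit from some of them. The loss is also selective: the subjects concerned are those with a breakthrough infection or another medical reason for not being dosed.

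**Working it through.** The plan gives no figure to reproduce here. The check traces one subject through the schedule and then counts days.

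**1. Path of a subject who consents at Visit 6 and is not dosed**

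- Footnote m: Visit 7 is skipped. The protocol's notes for the reader define *must* as always mandatory, and Section 8 allows no waivers. On the literal text, a site that held Visit 7 would be deviating.
- Footnote o: the subject is on Table 2a from consent.
- Table 2a: Visit 8 may or may not be attended. Visits 9 to 12 have no date, and Visit 12 is that table's end-of-trial visit.
- Section 7.1.1: *should* is defined as a recommendation, and on footnotes m and o the schedule it points to is one without Visit 7.

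Footnote h gives a different start for Table 2a but does not lift the skip in footnote m. The text is therefore inconsistent on when the schedule changes, while its only explicit instruction on Visit 7 is to drop it.

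**2. Length of the gap**

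Inputs: Visit 6 at Day 85±10 and Visit 7 at Day 182±20 (Table 2); Visit 8 at 3 to 7 months after injection 1 (Table 2a); 1 month = 30.25 days, and study day = days since injection 1, plus 1 (SAP 6.1.2).

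*Visit 8 not held.* From Visit 6 to nominal Day 182:

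- nominal: 182 − 85 = 97 days; 97/182 = 53%
- Visit 6 at its latest: 182 − 95 = 87 days; 87/182 = 48%
- Visit 6 at its earliest: 182 − 75 = 107 days; 107/182 = 59%

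*Visit 8 held, subject turned away.*

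- Window: 3 × 30.25 = 90.75 and 7 × 30.25 = 211.75 days, so whole days 91 to 211, which is Day 92 to Day 212 (121 days).
- On Day 92: 182 − 92 = 90 days remain. On or after Day 182: 0 days remain.
- The Visit 7 window, Day 162 to 202 (41 days), lies wholly inside the Visit 8 window, with 162 − 92 = 70 days before it and 212 − 202 = 10 days after it (70 + 41 + 10 = 121).

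These are calendar counts, not risks.

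**3. Number of subjects**

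Protocol 4.1 plans 15 transplant subjects, so the range is 0 to 15. The upper end is loose. The Dose 2 schedule came with version 4.0, dated 20 January 2022. A subject could use the Visit 6 route only if still within Day 95, that is, at most 94 days after injection 1. Counting back 94 days gives 18 October 2021, or later once approval time is allowed for. The planned start was June 2021. Actual injection dates are not given, so the range cannot be narrowed.

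**4. What a substitute contact can supply**

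Section 1.3 allows extra contacts: "The investigator may schedule visits (unplanned visits) in addition to those listed in the SoAs". For the titer this does not close the gap, because SAP 6.1.2 states: "Unscheduled visits will not be included in the summary tables but will be included in the listings". The SAP also has no rule that assigns a Visit 8 or Early Termination sample to Week 26 after Dose 1.

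**The case against.** The best reply is that footnote h governs. If Table 2a begins only after the second vaccination, an undosed subject stays on Table 2, and Section 7.1.1, which lists worsening health at the time of injection among its reasons for stopping IMP, points to a table that contains Visit 7. Footnote m, on this view, was simply not written with an undosed consenter in mind. That reading is reasonable and may well be what was intended. It shows that the text conflicts with itself. It does not restore the visit, because the skip in footnote m carries no condition and Section 7.1.1 only recommends.

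The second reply is that SAP 1.2 does not say its ineligible subjects had already consented at Visit 6. That stands. A subject found ineligible before consenting, or one who consents at Visit 7, keeps Visit 7. The gap needs consent at Visit 6 followed by no dose. The documents make that sequence possible but do not describe it.

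The third reply is that much still operates: Visit 8 if attended, with adverse event recording and a pre-dose titer; an Early Termination visit in both tables; unplanned visits; the hotline; follow-up of events already reported; and SAE/AESI reporting within 24 h of knowledge. A reader might infer from the missing visit that these subjects have no safety follow-up. The documents do not support that. What they lack is a dated inquiry at Week 26: the Early Termination visit is for discontinued subjects, if possible, and is not tied to Week 26, and the other routes depend on someone raising an event or choosing to call the subject in.

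**Conclusion.** The point holds as a minor defect in a stated scheduling rule. As written, a transplant subject who consents to Dose 2 at Visit 6 and is then not dosed has no assured Week 26 post-Dose-1 visit. The number affected lies between 0 and 15, is unknown, and may be zero. The nominal gap to Day 182 is 97 days if Visit 8 is not held, and 90 days down to nil if it is.

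This rests on reading footnotes m and o literally, on at least one subject following that path, and on the SAP's 30.25-day month for the Visit 8 window.

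Two stronger conclusions might be drawn and should not be. One is that 97 days, or 15 subjects, is what to expect: each is the unfavorable case, and the documents give no data on either. The other is that these subjects drop out of the primary analysis. They remain in the Safety Set, whose size is the default denominator for percentages (SAP 6.1.1). The effect on SAEs and AESIs is less systematic ascertainment. For the titer it is a missing Week 26 value in the summary tables. The trial is descriptive and tests no hypothesis, so no error rate or power is involved.

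**What to change.** Make the skip depend on dosing, and align the three footnotes.

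- **Footnote m, skip rule:** Visit 7 is held at Day 182±20 unless injection 2 has been given before it. No CMI sample is drawn while injection 2 is still planned.
- **Footnote m, last sentence, and footnote o:** Table 2a applies from administration of injection 2 (Visit 8), in line with footnote h.

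Changing the skip rule alone would not be enough, because footnote o would still move a consenter to a table without Visit 7.

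The cost is a footnote amendment, which needs ethics committee approval before use (Protocol 10.1.1), and one visit already in Table 2, with a 15 mL draw, for subjects not dosed by then. Some of these will be dosed later and would attend Visits 7 and 8 close together: at most 212 − 162 = 50 days apart, and possibly within days. Nothing changes for subjects dosed before Visit 7.

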BMI	Body Mass Index
CMI	Cell mediated immune (response)
COVID-19	Coronavirus Disease 2019
CRF	Case Report Form
CRO	Contract Research Organization
d	Day(s)
EDC	Electronic Data Capture (system)
ELISA	Enzyme-Linked Immunosorbent Assay
EOT	End Of Trial
FDA	Food and Drug Administration
FSH	Follicle Stimulating Hormone
GCP	Good Clinical Practice
h	Hour(s)
HIV	Human Immunodeficiency Virus
HLA	Human Leukocyte Antigen
HRT	Hormonal Replacement Therapy
IB	Investigator's Brochure
ICF	Informed Consent Form
ICH	International Conference on Harmonisation (of technical requirements for registration of pharmaceuticals for human use)
IEC	Independent Ethics Committee
IM	Intramuscular(ly)
IMP	Investigational Medicinal Product
ISF	Investigator's Site File
LNP	Lipid nanoparticle
min	Minute(s)
mRNA	Messenger RNA
NAAT	Nucleic Acid Amplification-based Test
NATAB	Neutralizing antibody titers and antibody binding
PBMC	Peripheral Blood Mononuclear Cells
pVNT	Pseudo viral neutralization test
PT	Preferred Term
RBD	Receptor Binding Domain
RNA-LNP	RNA-lipid nanoparticle
SAE	Serious Adverse Event
SAP	Statistical Analysis Plan

Abbreviation	Explanation
SARS-CoV-2	The virus leading to COVID-19
SRC	Safety Review Committee
SoA	Schedule of Activities
SOC	System Organ Class
SUSAR	Suspected Unexpected Serious Adverse Reaction
TCR	T-cell receptor
TEAE	Treatment Emergent Adverse Event
US(A)	United States (of America)
VOC	Variant Of Concern
VOI	Variant Of Interest
WHO	World Health Organization
WOCBP	Women Of Childbearing Potential

NOTES FOR THE READER

When the term "must" is used, the action/item is always mandatory. Non-compliance with this instruction constitutes a protocol deviation. When the term "should" is used, the action/item is recommended but not mandatory. Non-compliance with this instruction does not constitute a protocol deviation.

BNT162b2s01 is also referred to as BNT162b2 (B1.351).

Page 27 of 91 Version: 4.0 Date: 20 JAN 2022

2 INTRODUCTION

2.1 Background

2.1.1 Overview of the disease

By November 2019, the Severe Acute Respiratory Syndrome (SARS) -CoV-2 infection responsible for Coronavirus Disease 2019 (COVID-19) was documented in humans. By March 2020, the World Health Organization (WHO) characterized the COVID-19 outbreak as a pandemic.

Since the SARS-CoV-2 viral sequence was first determined, studies demonstrate how it continues to evolve in humans (through recombination, suboptimal immune control, etc.), resulting in a variety of VOC. In addition to mutations, additions or deletions near the receptor binding domain (RBD) of the Spike protein, which is responsible for attaching to the human angiotensin cell receptor 2 and resulting in host infection, other key changes (e.g., deletions) circumventing antibody detection (e.g., around Y144 in the N terminal domain) are increasingly recognized. More specifically, newer mutations of the Spike protein not only provide the virus with greater transmissibility and affinity/avidity for cellular attachment but may also render the VOC less susceptible to virus neutralization, thus allowing increases in overall infection rates. Because successful prophylactic COVID-19 vaccines are designed to primarily work by inducing neutralizing antibodies, an increased sense of urgency has again risen to anticipate and combat SARS-CoV-2 evolution through numerous tactics including characterization of the evolving sequences of SAR-CoV-2 with respect to vaccine-induced immune response breadth and durability with respect to key functional immune responses.

An overview to the more widely recognized SARS-CoV-2 variants of concern and interest is provided in Table 4.

Variant of concern or interest	WHO label	Pango lineage	GISAID clade / lineage	Next strain clade
VOC	Alpha	B.1.1.7	GRY	20I (V1)
VOC	Beta	B.1.351	GH/501Y.V2	20H (V2)
VOC	Gamma	P.1	GR/501Y.V3	20J (V3)
VOC	Delta	B.1.617.2	G/478K.V1	21A
VOC	Omicron	B.1.1.529	GRA	21K, 21L 21M
VOI	Lambda	C.37	GR/452Q.V1	21G
VOI	Mu	B.1.621	GH	21H

Table 4: Representative SARS-CoV-2 variants tracked by the WHO

VOC = A SARS-CoV-2 variant that meets the definition of a VOI (see below) and, through a comparative assessment, has been demonstrated to be associated with one or more of the following changes at a degree of global public health significance: Increase in transmissibility or detrimental change in COVID-19 epidemiology; or increase in virulence or change in clinical disease presentation; or decrease in effectiveness of public health and social measures or available diagnostics, vaccines, therapeutics.

VOI = A SARS-CoV-2 variant with genetic changes that are predicted or known to affect virus characteristics such as transmissibility, disease severity, immune escape, diagnostic or therapeutic escape; AND identified to cause significant community transmission or multiple COVID-19 clusters, in multiple countries with increasing relative prevalence alongside increasing number of cases over time, or other apparent epidemiological impacts to suggest an emerging risk to global public health.

DiaNTach SE	Clinical Trial Dratacal	Page 28 of 91
		Version: 4.0
Confidential	BN1162-14	Date: 20 JAN 2022

Abbreviations: GISAID = Global Initiative on Sharing Avian Influenza Data; VOC = variant of concern; VOI = variant of interest; WHO = World Health Organization.

Source: WHO webpage https://www.who.int/en/activities/tracking-SARS-CoV-2-variants/, accessed 27 DEC 2021.

